Meditation can prove challenging, however, especially for the neurologically injured who suffer from persistent inattention and distractibility. A recently launched consumer product, "MUSE: the brain-sensing headband" aims to facilitate meditation practice, cueing users into the success of their technique and helping them stay motivated to sustain a consistent practice (www.choosemuse.com). MUSE is a neurofeedback (NF) device that uses frontotemporal scalp electrodes to measure synchronous, postsynaptic potentials in the cortex represented as oscillatory EEG waves. These waves are mathematically transformed into an auditory neurofeedback signal that is fed back to users, training them to maximize relaxed, attentive and minimize distracted states of mind. Neurofeedback generally works through operant conditioning, enabling individuals to learn to control and/or change their brain activity over extended practice. User's performance and progress is tracked over time on a mobile device. By providing users with real-time feedback and gamifying their practice, MUSE aims to make meditation a more appealing and sustainable practice. These features may be of special relevance for the mTBI population.

In our study, we wish to evaluate the efficacy of a simple MM intervention in chronic TBI patients, evaluating its potential impact on anxiety, depression, and attention. Our study will involve two groups of patients, those who practice regular MM and those whose MM is enhanced by NF. We hypothesize that MM both with and without NF-assistance will lead to improvements in anxiety and depression scales. We further hypothesize that by optimizing a MM practice, MM-NF will lead to improvements in attention, as well as improved receptivity of the practice overall.

Previous clinical studies of MM on anxiety and mood:

In the last several decades, numerous studies have established the efficacy of MM in the treatment of mood disorders. A recent meta-analysis concluded that mindfulness-based therapies can reduce symptoms of anxiety and depression, with large effect size in patients with anxiety and depressive disorders and moderate effect size in the more general population (Hofmann 2010). The benefits of MM on anxiety and mood would likely extend to symptoms

within the mTBI population as well. Mood disturbances following TBI is very common, with cumulative rates of depression estimated at 61% and anxiety at 70% (Hibbard et al. 1998).

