A handful of studies have evaluated the impact of MM on mood disturbances in TBI. A pilot study employing a group mindfulness-based intervention in a TBI population showed improvements in quality of life after 12 weeks (Bedard et al. 2003). Improvements were maintained at follow-up one year later (Bedard et al. 2005), however no control patients were included in this latter study, making passage of time and/or placebo effects a possible explanation for the findings.

Attention in TBI—cognitive training and mindfulness-based training:

Attention training for the chronic TBI population is a domain of cognitive rehabilitation that has received a lot of consideration in recent years. Several large reviews and meta-analyses (Cicirone 2011; Ponsford 2014) similarly conclude that chronic, post-TBI attentional deficits can be at least partially rehabilitated through repetitive, task-based training.

Within the TBI literature, the modality with the most robust and promising literature is a cognitive strategy, Attention-Process Training (APT), a computer training game designed for patients with acquired brain injury that aims to rehab multiple subcomponents of attention. The concern with APT is despite improved performance on program tasks, training may not transfer to novel cognitive tests (Zickefoose, et al. 2013). Two small studies, however, have shown that improvements on APT do transfer to novel attentional tasks as measured by standard neuropsychological tests (Palmese et al. 2000; Pero et al. 2006). A more rigorous study of APT is currently being undertaken (Bartfai et al. 2014).

A growing body of evidence has examined the role of mindfulness meditation as a method of attention training in adults. Contemporary definitions of meditation define the practice as “attentional regulatory training” (Lutz et al. 2008). Studies have shown improvements following MM in executive attention (Tang et al. 2007; Wenk-Sormaz 2005; Ainsworth 2013) and attentional discrimination (Semple et al. 2010). Such studies compare pre- versus post-MM outcomes on objective neuropsychological tests—suggesting that MM does in fact transfer to novel tasks. On the contrary, a substantial number of studies have also failed to show MM to be beneficial to attention training (Anderson et al. 2007; MacCoon et al. 2014).

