MM represents a safe strategy for treating mood and anxiety disorders and potentially aspects of attentional performance in a mTBI population. However due to this population’s post-traumatic cognitive impairments, MM is a less accessible therapeutic strategy than it otherwise would be. MUSE, through its provision of NF and gamification, has the potential to help TBI patients initiate, sustain, and maintain a meditation practice. If MUSE outperforms MM on affective or cognitive outcome measurements, this study could function as a pilot study, informing future investigations of the product. If MUSE ultimately holds up in more rigorous studies, it should be recommended as a therapeutic tool to mTBI patients. If on the other hand, MUSE does not show any benefits over a regular practice of MM, the device would not be considered cost-effective and should therefore not be recommended to mTBI patients.

Specific Aims:

Aim 1: Evaluate within group differences, whether a daily, six-week practice of NF-MM or MM or a no-treatment control leads to pre- versus post-treatment changes in affective, cognitive, or mindfulness-associated variables.

Aim 2: Evaluate across-group differences, whether NF-MM outperforms MM in affective, cognitive, or mindfulness-associated variables, or whether NF-MM or MM differ from a no-treatment control group.

Aim 3: Evaluate the change in mindful attention (as measured by EEG) between NF-MM and MM groups and the no-treatment control group at the end of the intervention.

Aim 4: Evaluate the relationship between the degree of mindful attention (as measured by EEG) and affective and cognitive variables across NF-MM/MM groups as well as the no-treatment control group.

Aim 5: Evaluate acceptability of and attitudes toward NF-MM in TBI patients.

Subject Selection

Inclusion criteria: 1) history of mild-moderate TBI (per ACRM guidelines), 2) significant complaint of impaired attention or concentration, 3) ages 18-65, 4) >1 year since TBI, 5) significant cognitive function to participate in neurofeedback and mindfulness meditation, 6) has daily access to a smart phone, 7) no significant medication changes planned for the duration of the study, 8) has not had a significant meditation practice in the past.

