Treatment assignment and randomization, if applicable: Patients meeting study criteria will be randomized into one of two groups, either the NF-MM or MM group on a rolling admission. Preliminary assessment after 10 subjects enrolled in the study, demonstrated that participants in the intervention (MUSE) group had higher rates of depressive symptoms than participants in the control group. In order to balance these groups, we subsequently have decided to stratify by depression scores, such that the next five enrolled participants would be placed in the MUSE group if they had lower than average (for the study) BDI scores or the control group if they had higher than average (for the study) BDI scores. After these five subjects were enrolled, we will recalculate average BDI scores and decide whether to continue to stratify by depression scores or not.

Additionally, we have decided to add a no-treatment control group of 10 subjects. These individuals will be recruited after the first 20 subjects complete the trial. Thus, 30 subjects in total will now be part of this study.

Study Procedures

Study Site: Pre- and post-treatment assessments will be performed in outpatient offices at SRH in Charlestown or Cambridge (for those enrolled in the SRH study). MUSE training session will occur during the pre-treatment assessment session for the intervention groups. This training will last approximately 30 minutes and include a MM session with or without auditory NF.

Participants will then perform their 6 weeks of NF-MM with MUSE or MM without MUSE at their homes. Study staff will also call participants on a weekly basis, to remind patients to practice and provide technical support. A post-treatment assessment session will take place within one week of completion of the intervention. Those in the no-treatment control group, will simply undergo pre- and post-neuropsychological testing 6 weeks apart and receive meditation and MUSE training at their final 6-week visit.

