- 4) Qualitative assessment: Both NF-MM and MM groups will undergo a very brief qualitative interview at their post-treatment session to inquire on their subjective experience with MM with or without NF. The MM will then receive a MUSE device and practice NF-MM for two additional weeks, after which point they will receive a phone call with further questioning regarding their experience with MM with or without NF.

Biostatistical Analysis

First, we will power this study using the effect size that we calculate from the cognitive MUSE data collected by Bhayee et al. Then, we will compare our NF-MM, MM, and no-treatment control groups. We will contrast the three groups' cognitive outcomes in trail-making, symbol-digit coding, WAIS-IV digit spans. We will then compare affective outcomes using the Beck Anxiety Inventory, Beck Depression Inventory and Neurobehavioral Symptom Inventory. Finally we will compare mindfulness data from the Cognitive and Affective Mindfulness Scale. The continuous variables from the cognitive and affective measures will be analyzed with linear regression. The statistical contribution of demographic variables will be assessed using mixed effects models. We plan to perform post-hoc analysis for multiple comparisons.

Risks and Discomforts

Complications of procedures: We do not anticipate significant adverse effects from the use of MUSE technology, as it is already in wide use in the general population without reports of any significant harm. However, other neurofeedback studies have documented patient complaints of fatigue, feeling "spacey," anxiety, irritability, headache, or difficulty falling asleep (Hammond et al. 2011). Subjects will be able to contact study staff during daytime hours with questions or concerns regarding the possibility of such adverse effects. If these symptoms are believed to be stemming directly from use of MUSE and are intolerable for patients, they will be instructed to discontinue participation in the study.

Device complications/malfunctions: While it is not expected, it is possible for the MUSE device to malfunction. Participants will be able to email or call with tech support questions during standard business hours. Study staff members will call patients back to troubleshoot. While

equipment malfunction could interfere with data collection, it will not put patients at any risk of harm.

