Potential benefits to participants: Based on the mindfulness meditation literature, participation in the NF-MM or MM arms of this study is likely to have a positive impact on a patient's mood, anxiety, and biological stress levels. It may also help with attentional impairment. Individuals in the no-treatment control group will continue with care as usual. They are not expected to benefit directly from participation in this study.

All participants in all groups will receive a Muse device in compensation for completing the study.

Potential benefits to society (e.g., increased understanding of disease processes): Information from this study could potentially be useful to mTBI patients on a population level. If NF-MM is shown to significantly outperform standard MM in terms of psychological and cognitive performance, mTBI patients and their clinicians may want to consider using MUSE following brain injury. If NF does not enhance participants' practice of MM, mTBI patients and their clinicians will want to recommend against the use of the device, as its cost does not bear out in improved outcomes. If the NF-MM or MM groups outperform the no-treatment control group, results will suggest that various types of meditation interventions may be useful for affective or cognitive symptoms in individuals with traumatic brain injury.

Monitoring and QA

Independent monitoring of source data: Study staff, physicians or psychologists, will be responsible for reviewing the accuracy and completeness of form entries, case documents, and informed consent.

Safety and outcomes monitoring: Safety and efficacy data will be reviewed on a weekly basis through email or phone correspondence between participants and either a physician or psychologist study staff member. If the practice of meditation or use of neurofeedback is causing significant psychological distress or physical discomfort, the patient will be advised to discontinue participation.

Adverse event reporting guidelines: All reports of adverse psychological and physical effects will be relayed directly to the study PI and to MUSE.

References:

<http://doi.org/10.1016/j.psychres.2013.09.002>

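### Aim 1 puts a causal question to within-arm pre-post change, leaving room to credit meditation or neurofeedback with change that comes from retesting, time or expectancy

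*Combined protocol and SAP*

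**What the plan says.** Under Specific Aims, Aim 1 is to "Evaluate within group differences, whether a daily, six-week practice of NF-MM or MM or a no-treatment control leads to pre- versus post-treatment changes" in the affective, cognitive and mindfulness measures. Aim 2 makes the between-group comparison on the same measures: "whether NF-MM outperforms MM in affective, cognitive, or mindfulness-associated variables, or whether NF-MM or MM differ from a no-treatment control group". The plan gives no order of precedence between the two.

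The affective hypothesis in Background and Significance has the same form as Aim 1 and names no comparator: "We hypothesize that MM both with and without NF-assistance will lead to improvements in anxiety and depression scales".

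Biostatistical Analysis describes group comparisons only. It says "We will contrast the three groups' cognitive outcomes in trail-making, symbol-digit coding, WAIS-IV digit spans", then turns to affective and mindfulness outcomes. The method is brief: "The continuous variables from the cognitive and affective measures will be analyzed with linear regression". It does not say whether the dependent variable is the post-treatment score or the change, or whether baseline is a covariate. No within-arm test is named and no method is assigned to Aim 1.

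Under Study Procedures, the untreated subjects "will simply undergo pre- and post-neuropsychological testing 6 weeks apart". The randomization paragraph says they are recruited once the first 20 subjects have completed the trial. The same paragraph places five subjects by BDI score: below the study average to MUSE, above it to the control group.

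**The concern.** The affective and cognitive measures are taken twice, about six weeks apart, and the plan mentions no alternate test forms and no correction for practice. Cognitive scores can rise on a second sitting without treatment. Self-rated mood can improve with time or expectation. A pre-post test in one arm picks up all of this together with any effect of meditation.

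The protocol accepts the principle. In reviewing an uncontrolled follow-up study of mindfulness in brain injury, it notes that the lack of controls was a weakness, "making passage of time and/or placebo effects a possible explanation for the findings". Aim 1, read alone, offers no more protection than that.

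Two misreadings are possible. A significant gain in a meditation arm could be reported as support for the affective hypothesis, which as worded needs no comparator. And if one meditation arm reaches significance while the other does not, this could be taken as a neurofeedback effect, although the two arms have not been compared.

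**Working it through.** **The plan's own figure.** The total of 30 is 20 + 10. It cannot be reproduced as a power calculation, because no alpha, power, effect size, SD or dropout is stated.

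**Inputs.** From the documents: 20 subjects across NF-MM and MM, 10 untreated. Assumed: 10 in each meditation arm, two-sided 5% tests, no treatment effect, and the same non-treatment gain d (in baseline SDs) in every arm. Also assumed is a pre-post correlation r of 0.5 to 0.8. The documents give neither d nor r.

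**Within-arm test.** With equal SDs before and after, the SD of change is sqrt(2(1 − r)), so dz = d / sqrt(2(1 − r)). The paired t statistic on 10 subjects is noncentral t with 9 df and noncentrality dz × sqrt(10); the critical value is 2.262. Let p be the total rejection probability and u its upward part. Exactly one of two arms is significant upward with probability 2u(1 − u). For d = 0.3:

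| r | SD of change | dz | Noncentrality | p | u | 2u(1 − u) |
|---|---|---|---|---|---|---|
| 0.5 | 1.000 | 0.300 | 0.949 | 13.6% | 13.4% | 23% |
| 0.7 | 0.775 | 0.387 | 1.225 | 19.5% | 19.4% | 31% |
| 0.8 | 0.632 | 0.474 | 1.500 | 26.9% | 26.9% | 39% |

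The reference with no gain is p = 5% and 2 × 0.025 × 0.975 = 4.9%.

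The result depends on the assumed gain. Over r = 0.5 to 0.8, p runs from 8.8% to 14.6% at d = 0.2 and from 29.3% to 60.6% at d = 0.5.

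**Does the untreated arm inside Aim 1 settle it?** Not if the results are only set side by side. At d = 0.3 and r = 0.7, a given meditation arm is significant while the untreated arm is not with probability 0.195 × (1 − 0.195) = 15.7%.

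**Between-arm test.** A gain shared by both arms cancels. In 100,000 simulations at r = 0.7, a two-sample test of change rejected in 4.9% of trials at d = 0.3 and 5.0% at d = 0.5.

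**Price in power.** With 10 v 10 and a true difference of 0.5 SD, baseline adjustment at r = 0.7 gives a standardised difference of 0.5 / sqrt(1 − 0.49) = 0.70. The noncentrality is 0.70 × sqrt(10/2) = 1.57, and power is about 32%. Without baseline adjustment it is 18.5%.

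**The case against.** The strongest reply is that the plan does not rest efficacy on Aim 1. Aim 2 is between-group and so is Biostatistical Analysis. The stated conclusions are too: the rationale turns on MUSE outperforming MM, and Potential Benefits says "If the NF-MM or MM groups outperform the no-treatment control group, results will suggest" that meditation may be useful. No section draws a conclusion from within-arm change. All of this stands. A reader might infer that the trial plans to claim benefit from pre-post tests, or that it repeats the flaw it criticises in the uncontrolled study. The documents support neither: this trial has an active comparator and an untreated group.

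The untreated arm is also part of Aim 1 and is retested on a similar schedule, so it can show change without meditation. That is a partial safeguard. The arm is recruited later and not randomised, and setting separate tests side by side is not a comparison.

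Regression to the mean as a general explanation does not stand. Entry is by complaint, with no score threshold, and injury is more than a year old. The one support is the BDI-based placement of five subjects. Low scorers placed in MUSE would tend to drift up and high scorers placed in the control group down, moving within-arm BDI change in opposite directions.

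Finally, a study that may serve as a pilot can reasonably report change within each arm. That is an argument for keeping Aim 1 as description, not for its causal wording.

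**Conclusion.** The point holds as a risk of misreading that the plan leaves open. Aim 1 and the affective hypothesis are worded so that pre-post improvement alone would satisfy them. No sentence subordinates Aim 1 to Aim 2 or says what a within-arm result may be used for.

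On the stated assumptions with a shared gain of 0.3 SD, the nominal 5% within-arm error rate becomes 14% to 27%. The chance that exactly one meditation arm shows a significant gain rises from 5% to between 23% and 39%. These figures show scale and do not predict this trial's results: the gain, the correlation and the equal split of the first 20 subjects are all assumed. The between-arm test keeps its 5% level only for change that the arms share. Expectancy that differs between arms would remain.

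The weakness is inexpensive to correct and should be corrected before results are reported.

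**What to change.** - **Specific Aims, Aim 1:** label it descriptive. Report mean change with a 95% CI per arm, drop the causal verb, and make no efficacy claim from it.
- **Biostatistical Analysis:** base efficacy on between-arm contrasts of post-treatment score adjusted for baseline. Use NF-MM v MM for the added effect of neurofeedback. Use each meditation arm v no treatment for the hypothesis that meditation itself helps, labelled non-randomised and non-concurrent. Both kinds of contrast are needed, because a benefit shared by NF-MM and MM cancels when they are compared with each other. For the BDI outcome, baseline adjustment also addresses the score-based placement of five subjects.
- **Add one sentence:** differing within-arm significance is not evidence of a difference between arms.

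This takes a few sentences and no new data, since the baseline scores are already collected. It also settles whether baseline enters the regression. The real cost is fewer nominally positive results: with about 10 per arm, power for a 0.5 SD difference is only about 32% (baseline-adjusted, r = 0.7), so estimates and intervals should carry the report.

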Exclusion criteria: 1) severe mental illness or psychological symptoms (severe depression, suicidality, disabling anxiety, PTSD, psychosis, dissociation), 2) significant pre-morbid learning disability, 3) current or recent (in past year) history of significant drug or alcohol abuse, 4) medical illness severe enough to result in an attentional disorder, 5) neurodegenerative disease, 6) non-fluency in English.

Source of subjects/patients: Subjects will be recruited from a variety of settings including outpatient clinics and related clinical research projects of various clinicians including MDs,

SLPs, psychologists, and LCSWs at SRH and MGH, local TBI support groups, including BABIS (Boston Acquired Brain Injury Support Group), or the general population.

Recruitment methods: Recruitment methods will include word of mouth and dear colleague letters, email, list servs postings, flyers, as well as online posting on the partners RSVP for Health, Process Notes from MGH Psychiatry, Spaulding Weekly Spotlight publication, MA psych association listserv, and various social media outlets including LinkedIn and Facebook. The actual documents disseminated through these various above listed avenues will include all approved study documents which include approved poster with graphics, approved poster text (without graphics if dissemination avenue does not allow graphics—i.e. with a list serv), approved bullet-pointed list of study highlights, approved dear colleagues text.

Subject Enrollment

Methods of Enrollment: Interested participants will be instructed to call or email study staff who will give the patients a brief overview of the study, then perform a telephone or an online pre-screening.

Procedures for obtaining informed consent: Consent will initially be discussed with participants over the phone. On their initial pre-treatment visit, written consent will be obtained with either a study physician or psychologist.

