Device to be used: MUSE hardware and Calm app software. MUSE is a consumer product, a “brain-sensing headband” lined with 7 frontotemporal EEG sensors that detect alpha, beta, delta, gamma, and theta waves. MUSE training begins with a calibration task whereby participants’ EEG waves are compared between an attentional and relaxation task. The Calm app guides participants through a mindfulness meditation exercise, providing instructions for users to close their eyes, relax their body, and pay careful attention to their breath. During this meditative practice, EEG signals are fed back to patients through auditory feedback, a calm

versus noisy wind. When participants are consistently in a relaxed state, they will hear birds chirping. Through this auditory feedback, patients are trained to maximize their relaxed, attentive states, and minimize their distracted, tense states. User's performance and progress is tracked over time on a mobile device. MM controls will use a custom version of the Calm software for directed meditation without the MUSE EEG NF component. For further details regarding details of the MUSE device, please see attached documents.

Data to be collected:

- 1) Outcome measurements:
 - a. Cognitive assessments: Trail-Making Test (from D-KEFS), Symbol-Digit Coding, WAIS-IV Digit Span (forward, backward, sequencing), the Connor's Continuous Performance Test 3rd version (CPT-3), and the Self Efficacy (SEsx) scale.
 - b. Affective assessments: 1) Beck Anxiety Inventory (BAI), 2) Beck Depression Inventory (BDI-II), 3) Neurobehavioral Symptom Inventory (NSI)
 - c. Mindfulness assessment: Cognitive and Affective Mindfulness Scale – Revised (CAMS-R)
- 2) Compliance to intervention: The Calm app will track daily meditation practice adherence in both the NF-MM and the MM groups.
- 3) EEG data for NF-MM or MM groups: The Calm app will track the percentage of time participants in the NF-MM group spend in a relaxed attentive state during training. Additionally at the end of the 6-week intervention, both NF-MM and MM groups will be asked to meditate while connected to EEG leads without auditory neurofeedback. The percentage of time spent in a calm, neural, and active state will be assessed here as well.

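### NF-MM against MM is called randomised, but participants 11-15 (and possibly 16-20) are placed by BDI score with no random element, and baseline BDI is not pre-specified as a covariate

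*Combined protocol and SAP*

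**What the plan says.** Under Treatment assignment and randomization (Subject Enrollment), the plan states: "Patients meeting study criteria will be randomized into one of two groups". It then reports that after 10 enrolments the MUSE arm showed more depressive symptoms, and continues: "In order to balance these groups, we subsequently have decided to stratify by depression scores". The rule is that "the next five enrolled participants would be placed in the MUSE group if they had lower than average (for the study) BDI scores"; those above the average go to control. On what follows: "After these five subjects were enrolled, we will recalculate average BDI scores and decide whether to continue to stratify by depression scores or not". No criterion for that decision is given.

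The same section adds 10 no-treatment controls after the first 20 participants complete, for a total of 30. Data to be collected lists the BDI-II among the affective outcomes. On consent: "On their initial pre-treatment visit, written consent will be obtained with either a study physician or psychologist". The Biostatistical Analysis section says: "The continuous variables from the cognitive and affective measures will be analyzed with linear regression". It names no covariates for that regression, mentions only demographic variables for the mixed models, and does not say whether the outcome is the post-treatment score or the change.

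**The concern.** Stratified randomisation still randomises within the high and low strata. Here the score fixes the arm. Three things follow.

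- **Label.** The NF-MM against MM contrast in Aim 2 is only partly randomised, although the plan's terms are randomised and stratified.
- **Foreseeability.** Anyone who knows the score and the running average knows the arm. Consent is taken at the pre-treatment visit, where the BDI-II is also completed, and their order is not stated. An effect on who enters is possible but not shown.
- **Analysis.** The allocation variable is also an outcome. Without a baseline term, any remaining BDI imbalance pushes the result one way on post score and the other way on change, and the plan leaves that choice open.

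**Working it through.** **The plan's own figure.** 20 + 10 = 30, which matches the stated total. No sample-size formula can be checked, because alpha, power, effect size and SD are not given.

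**Share placed by rule.** 5/20 = 25%; if continued to participant 20, 10/20 = 50%. The 20 is inferred from the timing of the no-treatment group.

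**Random element.** As written, the probability of MUSE is 1 below the average and 0 above it. A score equal to the average is not covered.

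**Size, for the BDI outcome only.** Assumptions not in the documents: normal BDI with SD 1, a 5:5 start with MUSE higher (the plan does not give the gap), placement by the running study mean, pre-post correlation r of 0.8 to 0.5, and no treatment effect. Let I be mean baseline BDI in MUSE minus MM, in SD. Simulated values at n = 20:

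| Allocation of 11-20 | Mean I | Mean absolute I, all starts | Mean absolute I, starts of 0.5 SD or more |
|---|---|---|---|
| Rule to 15, then simple randomisation | -0.13 | 0.28 | 0.24 |
| Simple randomisation throughout | +0.26 | 0.36 | 0.47 |
| Rule to 20 regardless | -0.53 | 0.54 | 0.37 |

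Without a baseline term, bias on post score = r × I, and bias on change = -(1 - r) × I. Lower BDI is better, so a negative bias favours MUSE.

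- *Rule to 15* (I = -0.134 before rounding). Post score: 0.5 × 0.134 = 0.07 to 0.8 × 0.134 = 0.11 SD in favour of MUSE. Change: 0.2 × 0.134 = 0.03 to 0.5 × 0.134 = 0.07 SD against. For starts of 0.5 SD or more (43% of runs), mean I is +0.05 and the directions swap.
- *Rule to 20 regardless* (I = -0.53). Post score: 0.5 × 0.53 = 0.27 to 0.8 × 0.53 = 0.42 SD in favour. Change: 0.2 × 0.53 = 0.11 to 0.5 × 0.53 = 0.27 SD against.
- *Adjusted for baseline BDI.* Bias is 0.01 SD or less in each case, with 95% coverage.

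**The open decision.** If the rule continues only when MUSE is still higher at n = 15 (26% of runs), mean absolute imbalance in those runs goes from 0.23 to 0.26 SD, about what randomising gives (0.25). If it continues only when MUSE is more than 0.2 SD higher, it falls from 0.40 to 0.17 SD (randomising: 0.33). The unstated criterion therefore decides whether continuing helps.

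**Scale.** With the rule to 15, the mean 95% half-width for the BDI contrast at n = 20 is 0.58-0.83 SD adjusted, against 0.59-0.94 SD for unadjusted change and 0.94 SD for post score.

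**The case against.** The plan hides nothing: the look, its reason, the rule, its limit of five and the re-check all follow directly after the claim of randomisation. Only the label is wrong. The stated aim is balance, and for large starting gaps the rule about halves the imbalance left by simple randomisation (0.24 against 0.47 SD). Stopped at 15, it leaves a bias that is small beside the interval width. Running to 20 regardless would ignore the planned re-check and work against the stated aim, so those figures are a worst case. Linear regression can include baseline BDI, and the plan does not rule it out. Aims 1 and 5 do not rest on this contrast, and the rationale says that "this study could function as a pilot study, informing future investigations of the product". All of this stands.

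It does not remove the point. Balance on one score does not make an allocation random or concealed. The continuation decision has no criterion. Leaving both the covariate and the form of the outcome open leaves the direction of any bias open. The pilot remark applies if MUSE outperforms; if it shows no benefit over MM, the same section says that the device should not be recommended, and that conclusion rests on this contrast.

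**Conclusion.** The point holds in a limited form and should be fixed. Five of 20 allocations in the main active comparison are non-random as written, continuation to 16-20 is uncontrolled, and the simple analytic protection is not pre-specified. The likely bias on BDI is small if the rule stops at 15 (0.03-0.11 SD) and reaches 0.42 SD only in the worst case. These sizes depend on the assumed distribution, starting gap and correlation. Nothing has been quantified for the cognitive or mindfulness outcomes.

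A reader might infer more, and the documents do not support it:

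- That the comparison is invalid or seriously biased. On the written rule for 11-15, it is not.
- That recruitment was influenced by foreseeable allocation. The order of consent and BDI-II is not given.
- That baseline BDI is excluded from the models. It is unspecified.
- That the rule distorts arm sizes. A split of 12-8 or worse occurs in 34% of runs under the rule to 20, and also in 34% under simple randomisation.

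**What to change.** 1. Pre-specify baseline BDI, plus the outcome's own baseline where that differs, as covariates in the NF-MM against MM models, and state whether post score or change is analysed. This costs one or two degrees of freedom. The gain in precision is shown for BDI only.
2. Delete the option to continue the deterministic rule. Allocate every NF-MM and MM participant not yet placed by a concealed method with a random element, for example minimisation on the difference in mean BDI with assignment probability below 1. At 80:20, under the same assumptions and for starts of 0.5 SD or more, mean absolute imbalance at n = 20 is about 0.16 SD if 11-20 are open and 0.12 SD if only 16-20 are. The main gain is unpredictability, at similar or better balance.
3. Report rule-placed participants as non-randomly allocated and describe NF-MM against MM as partly randomised. A sensitivity analysis without them is optional. It must be baseline-adjusted and will be imprecise: without 11-15, the half-width is 0.70-1.01 SD.

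The cost is one amendment, one or two model terms and a short allocation script, with no extra patients or visits. The past tense about enrolment suggests that 11-15 may already be placed. Items 1 and 3 then still apply in full, and item 2 applies to 16-20.
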